	
generate an immune response, including concomitant immune suppressive therapy
 
7. Immunosuppressive therapy:
 
a) Systemic immunosuppressive drugs including corticosteroids (prednisone equivalent >10 mg/day, http://www.medcalc.com/steroid.html) within 6 weeksb) Immune suppression/requiring immunosuppressive drugs, including subjects with organ allograftsc) Active autoimmune disease requiring the equivalent of >10 mg/day of prednisone 
8. Major surgery within 4 weeks of study treatment, or major surgery planned for duration of study participation
 
9. History of prior malignancy, unless the prior malignancy was diagnosed and definitively treated ≥ 5 years previously with no subsequent evidence of recurrence
 
NOTE: This does not apply to previous breast cancer, carcinoma in situ of the cervix, inactive melanoma or non-melanoma skin cancer, or Grade 1 papillary bladder cancer
 
10. Subjects with brain or subdural metastases, unless local therapy has completed and corticosteroids have been discontinued for this indication for ≥ 4 weeks before starting study treatment. Any signs (eg, radiologic) and/or symptoms of brain metastases must be stable for ≥ 4 weeks before starting study treatment; radiographic stability should be determined by comparing a contrast-enhanced computed tomography (CT) or magnetic resonance imaging (MRI) brain scan performed during screening to a prior scan performed at least 4 weeks earlier.
 
11. Any medications that induce, inhibit, or are substrates of cytochrome P450 (CYP450) 3A4 within 7 days prior to the first dose of study drug
 
12. Subjects with meningeal carcinomatosis
 
13. Known significant hypersensitivity to study drugs or excipients
 
14. History of malabsorption syndrome or other condition that would interfere with enteral absorption
 
15. International Normalized Ratio (INR) and activated partial thromboplastin time [PTT] $<1.5 \times$ ULN, if not therapeutically anticoagulated. Subjects who are being therapeutically anticoagulated with an agent such as Coumadin (warfarin sodium) or subcutaneous heparin may be included provided there is no prior evidence of underlying abnormality in coagulation parameters, screening test results are in appropriate therapeutic range, and anticoagulation regimen is stable and closely monitored.
 
16. New York Heart Association (NYHA) Class II or greater congestive heart failure OR active ventricular arrhythmia requiring medication

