Table 2A: Part 1, Cycle 1 ONLY [contains PK schedule]

Activity	Screening ¹ Day -28 to -1		Part 1 Cycle 1 ONLY					
	Pre- Registration	Post- Registration	Day 1	Day 2	Day 3	Day 7	Day 8	Day 15 ± 2 days
Clinical Assessments								
Informed Consent ²	X							
Medical/Cancer History ³	X							
Physical Exam ⁴	X		X					
ECOG PS ⁵	X		X					
Height	X							
Weight	X		X					
Vital Signs ⁶	X		X	X	X	X		X
Adverse Events ⁷	X							→
Concomitant Med. ⁸	X							→
Clinical Laboratory								
Pregnancy test ⁹	X		X					
Hematology tests ¹⁰	X		X			X		X
Serum Chemistry tests ¹¹	X		X			X		X
Urinalysis ¹²	X		X					X
ECG ¹³	X		X					
Subject Registration ¹⁴	X							
Pharmacokinetic Analysis^a								
INXN-1001			X	X		X	X	
Tumor Response/ Pharmacodynamic								
Imaging Studies/Tumor Assessment ¹⁵	X							
Serum cytokine profile & breast CA biomarkers ¹⁶		X			X			X
Digital photography ¹⁷		X						

Activity	Screening ¹ Day -28 to -1		Part 1 Cycle 1 ONLY					
	Pre- Registration	Post- Registration	Day 1	Day 2	Day 3	Day 7	Day 8	Day 15 ± 2 days
Study Drug Administration								
Intratumoral INXN-2001 ¹⁸			X					
Oral INXN-1001 ¹⁹				←	X	→		
Verify Adherence to INXN-1001 dosing ¹⁹							X	
Palifosfamide (IV), Arm C ²⁰			X	X	X			

^a **PK Sampling Schedule**

Samples for PK analysis of INXN-1001 for Part 1 CYCLE 1 ONLY should be obtained on the following days and time points:

Day 1: [6 samples] Pre-dose (\leq 30 minutes prior to INXN-1001 dosing), 0.5, 1, 2, 4, 6 hours post-INXN-1001 dosing

Day 2: [1 sample] Pre-dose (\leq 30 minutes prior to INXN-1001 dosing)

Day 7: [3 samples] Pre-dose (\leq 30 minutes prior to INXN-1001 dosing), 1-2 hours, 4-6 hours post-INXN-1001 dosing

Day 8: [1 sample] 24 \pm 3 hours post-Day 7 INXN-1001 dose

Table 2A numbered footnotes found after Table 2B (p.19)

Table 2B: ALL Cycles (EXCEPT for Part 1, Cycle 1 - see Table 2A)

Activity	Screening ¹ Day -28 to -1		ALL Cycles (EXCEPT for Part 1 Cycle 1 - see Table 2A)					Post-Treatment Safety Assessment Visit ²²	Follow-Up Tumor Assessment Visit ²³	
	Pre-Registration	Post-Registration	Day 1 ²¹	Day 2	Day 3	Day 7	Day 15 ± 2 days			
Clinical Assessments										
Informed Consent ²	X									
Medical/Cancer History ³	X									X ²⁴
Physical Exam ⁴	X		X						X	
ECOG PS ⁵	X		X						X	
Height	X									
Weight	X		X						X	
Vital Signs ⁶	X		X	X	X	X	X		X	
Adverse Events ⁷	X								X	
Concomitant Med. ⁸	X									X
Clinical Laboratory										
Pregnancy test ⁹	X		X							
Hematology tests ¹⁰	X		X				X	X	X	

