5.1 Inclusion Criteria

To be enrolled in the trial, each subject must satisfy all of the following inclusion criteria:

1. Males or females of all races \geq 18 years of age, who have provided written informed consent prior to completing any study-specific procedure.
2. Histologically or cytologically confirmed adenocarcinoma of the breast, either locally recurrent or metastatic disease with injectable lesions, for which no proven curative therapy exists. Locally recurrent disease must not be amenable to surgical resection or radiation with curative intent.
3. Subject has failed or progressed on at least 1 prior systemic chemotherapy regimen \pm biologic/experimental therapy (if first-line therapy, failure or progression during or within the first 30 days).
4. Resolution of all chemotherapy or radiation-related toxicities to Grade 1 severity or lower, except for stable sensory neuropathy \leq Grade 2 and alopecia.
5. A minimum of 2 lesion(s) assessed by imaging using mRECIST v1.1. 1 or more lesions NOT to be injected AND at least 1 injectable lesion(s) (eg, may use radiographically-guided injection of lesions if available at site)
6. Eastern Cooperative Oncology Group (ECOG) performance status 0, 1, 2
7. Male and female subjects must agree to use a highly reliable method of birth control (expected failure rate less than 5% per year) from the screening visit through 28 days after the last dose of study drug. Women of childbearing potential (perimenopausal

women must be amenorrheic for at least 12 months to be considered of non-childbearing potential) must have a negative pregnancy test at screening.

8. Adequate bone marrow reserve as indicated by:
 - a) Absolute neutrophil count (ANC) $> 1500/\mu\text{L}$ (without use of growth factors within 7 days)
 - b) Absolute lymphocyte count (ALC) $> 700/\mu\text{L}$ (without use of growth factors within 7 days)
 - c) Platelet count $> 100,000/\text{mm}^3$ (without transfusion in prior 7 days)
 - d) Hemoglobin $> 9.0 \text{ g/dL}$ (without transfusion in prior 7 days)
9. Adequate renal function as evidenced by eGFR using the Modification of Diet in Renal Disease (MDRD) equation: $\text{eGFR} \geq 60 \text{ mL/min}/1.73 \text{ m}^2$
10. Adequate liver function as evidenced by the following:
 - a) Bilirubin ≤ 1.5 times the upper limits of normal (ULN)
 - b) ALT and AST $\leq 2.5 \times \text{ULN}$, in the case of liver metastases $\leq 5 \times \text{ULN}$

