10. Subjects with brain or subdural metastases are not eligible, unless local therapy completed and corticosteroids discontinued for this indication for ≥ 4 weeks before starting study treatment. Any signs (eg, radiologic) and/or symptoms of brain metastases must be stable for ≥ 4 weeks before starting study treatment; radiographic stability should be determined by comparing a contrast-enhanced computed tomography (CT) or magnetic resonance imaging (MRI) brain scan performed during screening to a prior scan performed at least 4 weeks earlier.

NOTE: Screening for brain lesions by CT or MRI is not required for all potential subjects; however, if there are any neurological signs or symptoms consistent with brain metastases, then a brain CT or MRI should be performed as clinically indicated.

11. Any medications that induce, inhibit or are substrates of cytochrome P450 (CYP450) 3A4 within 7 days prior to the first dose of study drug

12. Subjects with meningeal carcinomatosis

13. Known significant hypersensitivity to study drugs or excipients

14. History of malabsorption syndrome or other condition that would interfere with enteral absorption

15. International Normalized Ratio (INR) and activated PTT $< 1.5 \times$ ULN, if not therapeutically anticoagulated. Subjects who are being therapeutically anticoagulated with an agent such as Coumadin (warfarin sodium) or subcutaneous heparin may be included provided there is no prior evidence of underlying abnormality in coagulation parameters, screening test results are in appropriate therapeutic range, and anticoagulation regimen is stable and closely monitored

16. New York Heart Association (NYHA) Class II or greater congestive heart failure OR active ventricular arrhythmia requiring medication

17. Any other unstable or clinically significant concurrent medical condition (eg, infection requiring systemic anti-infective agents) that would, in the opinion of the investigator, jeopardize the safety of a subject and/or their compliance with the protocol

18. Localized infection at site of injectable lesion(s) requiring anti-infective therapy within 2 weeks of the first dose of study drug

NOTE: Appropriate testing (eg, punch biopsy [PBx] with bacterial counts) must be performed to rule out infection in cases where the presence of infection is ambiguous or clinical signs of infection are evident.

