6.2.5 Retreatment Criteria, Dose Delays and Modifications

Subjects may receive up to 6 cycles of study drug treatment. To receive each repeat treatment cycle, all treatment-related AEs must have resolved to Grade 1 or baseline and the following laboratory criteria must be met:

Hemoglobin \geq 9 g/L	eGFR \geq 60 mL/min/1.73 m ²
Lymphocytes $>$ 700/ mm ³	AST and ALT \leq 2.5 x ULN For subjects with documented liver metastases, ALT and AST \leq 5 \times ULN
Neutrophils \geq 1,500/ mm ³	Total bilirubin $<$ 1.5 x ULN
Platelets \geq 100,000/ mm ³	INR and PTT $<$ 1.5 x ULN

Clinical laboratory tests drawn pre-treatment for analysis on Day 1 of each cycle may be used for determining if the re-treatment criteria have been met, and must be reviewed by the investigator or designee prior to the next cycle of study drug administration. Two treatment delays for recovery to acceptable levels are allowed at weekly intervals up to a maximum of 14 days. In the event that a treatment-related dose delay is necessary for palifosfamide, then the next cycle of study treatment will be administered at 80% of the dose ([Table 3](#)). If an AE is clearly related to 1 study drug and not the other (in combination Treatment Arm C), then dose modification/delay is to occur for the relevant study drug (INXN-1001 and/or palifosfamide). A maximum of two dose reductions, of either INXN-1001 or palifosfamide, will be allowed.

Table 3. Dose Modifications for Palifosfamide-related Toxicity^a

ADVERSE EVENT	PALIFOSFAMIDE
Hematologic	
Platelet count <100 × 10 ⁹ /L	Delay dose of palifosfamide up to 14 days until platelet count ≥ 100 × 10 ⁹ /L, then reduce by 20%.
ANC < 1500/mm ³	Delay dose of palifosfamide up to 14 days until ANC returns to ≥ 1500, then maintain dose when restarted.
Neutropenic fever	Delay dose of palifosfamide up to 14 days until resolved, then reduce by 20%.
Any Grade 4 hematologic toxicity	Delay dose of palifosfamide up to 14 days until Grade ≤ 1 or baseline, then reduce by 20%.
Estimated Glomerular Filtration Rate (eGFR) (Appendix 5)	
≥25% up to <50% decrease from baseline ^b	Hold dose until repeat test is performed. Reduce dose of palifosfamide by 20% if confirmed on repeat test.
≥50% decrease from baseline ²	Hold dose until repeat test is performed. Discontinue palifosfamide if confirmed on repeat test.
Non-hematologic (other than creatinine or urinary electrolyte wasting)	

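### Section 6.2.5 requires INR and PTT below 1.5 x ULN before every repeat cycle, with no exception for the therapeutically anticoagulated subjects whom exclusion 15 admits

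*Protocol*

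**What the plan says.** **Entry.** Exclusion 15 applies its 1.5 x ULN limit on INR and PTT only "if not therapeutically anticoagulated". Subjects on warfarin or subcutaneous heparin may be included if they have no prior underlying coagulation abnormality and "screening test results are in appropriate therapeutic range, and anticoagulation regimen is stable and closely monitored". Their entry standard is the therapeutic range, not 1.5 x ULN.

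**Retreatment.** Section 6.2.5 states that, for each repeat cycle, "the following laboratory criteria must be met", and one of those criteria is "INR and PTT $<$ 1.5 x ULN". No qualifier follows. The ALT/AST line of the same list does carry one: "For subjects with documented liver metastases" the limit rises to 5 x ULN. That mirrors inclusion 10, which allows the higher limit "in the case of liver metastases".

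**Delay.** Section 6.2.5 continues: "Two treatment delays for recovery to acceptable levels are allowed at weekly intervals up to a maximum of 14 days".

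**Measurement.** INR and PTT belong to the hematology panel (footnote 10 to Tables 2A and 2B; Section 6.4.2.8). The "Hematology tests" row of Table 2B schedules that panel on Day 1 of each cycle, so the values will be available when the rule is applied.

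**The concern.** The entry rule and the retreatment rule treat the same value in the same subject differently. A value in therapeutic range but at or above 1.5 x ULN is acceptable for the first injection and disqualifying for the second, although nothing need have changed in between. Because the list carries over the liver-metastasis allowance and not the anticoagulation allowance, the difference looks like an omission. The protocol gives no reason for a stricter limit from Cycle 2 on.

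At stake is whether a properly enrolled subject receives the planned treatment. Followed exactly, the rule leaves the site three courses: stop after one cycle, alter an anticoagulation regimen whose stability was a condition of entry, or deviate from the protocol.

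**Working it through.** The plan states no figure on this point, so the check sets the rules side by side, searches for a waiver, and then counts what a blocked subject would miss.

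**1. The two rules for a therapeutically anticoagulated subject**

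| INR or PTT | Exclusion 15 (before Cycle 1) | Section 6.2.5 (before Cycles 2 to 6) |
|---|---|---|
| Both in range, both below 1.5 x ULN | may enter | passes |
| In range, either at or above 1.5 x ULN | may enter | fails |

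Only the second row is in conflict. The first sentence of exclusion 15 has its inequality the wrong way round for an exclusion. That is a separate matter, and the sentence admitting anticoagulated subjects is clear without it.

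**2. Search for a waiver**

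- Section 6.2.5, return to Grade 1 or baseline: this applies to treatment-related AEs. The laboratory criteria are an additional requirement.
- Section 6.2.5, delays: 14 days at most, and intended for recovery. A value kept in therapeutic range on purpose is not expected to recover.
- Section 6.2.5, case-by-case re-exposure: limited to treatment-related Grade 4 AEs.
- Footnote 21: says which samples may be used, not which limits apply.
- Section 6.2.4.4: the Medical Monitor is consulted on delays for other reasons. No waiver is granted.
- Section 6.3: standard treatment of underlying illness is permitted, so changing the anticoagulant is not prohibited. Section 6.2.5 does not mention it.
- The SAP describes a one-cycle regimen and contains no retreatment rule.

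None of these lifts the limit.

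**3. Treatment not given if a subject is blocked from Cycle 2 on**

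Inputs: 6 planned cycles of 21 days. Each has 1 INXN-2001 injection, 7 daily INXN-1001 doses and, in Arm C, 3 palifosfamide infusions.

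- Injections: planned 6 x 1 = 6, given 1, not given 5 (5/6 = 83.3%).
- INXN-1001 doses: planned 6 x 7 = 42, given 7, not given 35 (35/42 = 83.3%).
- Palifosfamide infusions, Arm C: planned 6 x 3 = 18, given 3, not given 15 (15/18 = 83.3%).

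Cycle 2 is due on Day 21 + 1 = Day 22. The two weekly delays move it to Day 29 and then Day 36, the last permitted start.

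**4. Tumor assessments still due for that subject**

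- Last dose: Day 7, the final INXN-1001 dose of Cycle 1.
- Post-Treatment Safety Assessment, 28 ± 3 days after the last dose (footnote 22): Day 7 + 28 = Day 35, range Day 32 to 38.
- Follow-Up Tumor Assessment, 35 ± 7 days after that visit and required of every subject (footnote 23): Day 35 + 35 = Day 70. Earliest 32 + 28 = Day 60; latest 38 + 42 = Day 80.
- Week-12 and week-16 assessments, also for all subjects (footnote 15; Section 6.4.3). On the nominal calendar these are C5D1 = 4 x 21 + 1 = Day 85 and C6D7 = 5 x 21 + 7 = Day 112.

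**5. Who could be affected**

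The documents give neither a ULN nor a therapeutic range. Assuming a local INR ULN of 1.0 to 1.3, the limit lies between 1.5 x 1.0 = 1.50 and 1.5 x 1.3 = 1.95. A subject whose therapeutic range starts at or above that figure fails at every cycle while in range. A regimen that leaves both INR and PTT below their limits passes. The conflict in step 1 does not depend on this assumption.

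**The case against.** The strongest reply is that a retreatment rule need not copy an entry rule. It also screens for toxicity after exposure, which cannot exist before Cycle 1. The protocol supplies some background for such caution: Section 3.4.2 reports one subject with PTT prolongation in an adenoviral p53 trial, and Section 6.2.4.4 asks for careful hematologic monitoring with palifosfamide. The two lists also differ elsewhere: bilirubin may equal 1.5 x ULN at entry but must be below it for retreatment, and the neutrophil limit differs in the opposite way. A difference alone does not prove an oversight.

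This stands in part. A stricter limit after exposure is coherent, and it cannot be said that the entry allowance must be wrong. But the protocol states no such intent, and a fixed ceiling cannot distinguish a new toxicity from a value that the anticoagulant is meant to produce. Requiring values in therapeutic range and no new unexplained abnormality keeps the toxicity check without that fault.

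A second reply is that the consequence is small. The group may be empty, a change of anticoagulation is not prohibited, and Sections 4.1.5 and 5.4 let another subject be added when treatment stops before six cycles for a reason other than progression. All of this stands, and it limits the severity.

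A reader might go further and infer that a blocked subject goes unscanned until week 12, drops out of the Efficacy Evaluable Population, or is counted as not progression-free, and so moves the 16-week PFS decision. The documents do not support this. The assessment due at about Day 70 and the week-12 and week-16 scans apply to such a subject. Lacking any post-screening evaluation, or having an event-free last scan before week 16, would require a missed visit, dropout or death. Neither follows from the laboratory rule.

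**Conclusion.** The inconsistency is real on the text and nothing in either document resolves it. A therapeutically anticoagulated subject admitted with INR or PTT at or above 1.5 x ULN may receive Cycle 1 and, as the rule is written, cannot receive Cycles 2 to 6 unless the value is brought down or the site deviates. For each such subject who is blocked throughout, 83.3% of planned dosing is lost, including 5 of 6 injections. That is the worst case for one subject, not an estimate for the trial.

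The number affected is unknown and may be zero. It depends on local ULNs, therapeutic ranges and the anticoagulants in use, none of which the documents give. It would be wrong to infer that every anticoagulated subject is barred from retreatment: those below the limit are not.

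The effect shown is on treatment delivery. None is shown on the Simon design, the 16-week PFS decision or the analysis population. Severity: minor. It is worth correcting because the rule decides who is retreated and the correction is short.

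**What to change.** Extend the INR/PTT line of Section 6.2.5, in the manner of the ALT/AST line. Suggested wording: *INR and PTT < 1.5 x ULN if not therapeutically anticoagulated; anticoagulated subjects must be within their therapeutic range on a stable, closely monitored regimen, with no new unexplained coagulation abnormality since the previous cycle.*

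The downside is that some anticoagulated subjects will be re-injected at INR or PTT levels already permitted at Cycle 1. If the sponsor regards those levels as unsafe for intratumoral injection, the consistent course is to remove the anticoagulation allowance from exclusion 15, in both the synopsis and Section 5.2, because Cycle 1 carries the same injection. That costs a somewhat smaller eligible pool.

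Either change is a matter of one clause or one deletion at the next amendment. Neither adds tests, visits or subjects.

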6.2.3 Treatment Regimen

A combination of up to 3 investigational medications will be evaluated for safety, tolerability, efficacy, and biological effects in this trial. The small molecule INXN-1001 will be administered as oral capsules (once daily doses on Days 1-7) in combination with an IT injection of INXN-2001 (on Day 1 of each cycle). For each 21-day treatment cycle, INXN-2001 dosing will occur 3 hours \pm 30 minutes after the first dose of INXN-1001. INXN-2001 will be given as IT injections of approximately [REDACTED] 1 mL per treatment.

Following Cycle 1, if no accessible lesion for INXN-2001 injection is present (eg, due to complete resolution), then INXN-2001 should be injected into an alternate lesion or a draining, pathologic lymph node of a previously accessible lesion. A pathologic lymph node must be defined as a lesion per mRECIST ([Appendix 4](#)). The injections will be administered on the first day of each cycle throughout the study. Subjects must be adequately hydrated on each day of study drug administration. Subjects must be instructed to maintain good oral hydration on and between dosing days.

[REDACTED]

[REDACTED]

[figure not shown]
[REDACTED]

For treatment Arm C Combination

Therapy (Ad-RTS-hIL-12 + palifosfamide), palifosfamide will be administered following administration of INXN-1001 as a 30-minute IV infusion, and on Day 1 of each cycle the infusion should complete before injection with INXN-2001.

Palifosfamide will be administered intravenously at a dose of 120 mg/m²/day as a 30-minute infusion on Days 1, 2, and 3 of a 21-day cycle for up to 6 cycles.

The temporal sequence of the treatment regimens for study Arms A and C are shown in [Figure 4](#). For subjects enrolled in Arm C Ad-RTS-hIL-12 + Palifosfamide Combination Therapy, the sequence of regimens A + palifosfamide will be followed concurrently as shown below.

Figure 4. Study Arm Treatment Regimens**6.2.4 Preparation and Administration of Study Drug**

Please refer to the Pharmacy Manual for additional information.

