Not treatment-related Grade 3 if unresponsive to appropriate therapy.	Delay dose of palifosfamide for up to 14 days until Grade ≤ 1 or baseline, then reduce by 20%.
Not treatment-related Grade 4	Delay dose of palifosfamide up to 14 days until ≤ Grade 1 or baseline, then reduce by 20%.

^aWhen indicated, the maximum permitted delay of study drug administration due to toxicity and/or for confirmatory laboratory testing is 14 days.

^bBaseline eGFR determined based on the most recent serum creatinine measurement prior to study drug administration (ie, Cycle 1 Day 1 or Screening).

Subjects who experience a treatment-related Grade 4 AE, other than nausea and/or vomiting in the absence of optimal treatment with antiemetics, will be discontinued from study treatment. If, however, the subject has experienced a substantial benefit from treatment and the PI and Medical Monitor recommend continuation on the study, re-exposure to the experimental treatment may proceed on a case-by-case basis.

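### After a delay for treatment-related neutropenia (afebrile, below Grade 4), Protocol 6.2.5 gives palifosfamide at 80% in the text but at full dose in Table 3

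*Protocol*

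**What the plan says.** Palifosfamide is given only in Arm C, at 120 mg/m²/day by "infusion on Days 1, 2, and 3 of a 21-day cycle for up to 6 cycles" (Protocol 6.2.3). Four statements in Protocol 6.2.5 bear on the dose after a delay.

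- **The general sentence.** Its trigger is "In the event that a treatment-related dose delay is necessary for palifosfamide". Its consequence is "then the next cycle of study treatment will be administered at 80% of the dose", followed by a bracketed pointer to Table 3.
- **The ANC row of Table 3.** The table is titled "Dose Modifications for Palifosfamide-related Toxicity". For ANC below 1500/mm³ it allows a delay of up to 14 days for recovery to at least 1500, "then maintain dose when restarted".
- **The cap.** "A maximum of two dose reductions, of either INXN-1001 or palifosfamide, will be allowed".
- **The Grade 4 rule after the table.** "Subjects who experience a treatment-related Grade 4 AE" come off study treatment, apart from an exception for nausea or vomiting without optimal antiemetics and case-by-case continuation where there is substantial benefit.

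The retreatment criteria in the same section require neutrophils of at least 1,500/mm³, the same threshold as the ANC row. The Amendment 2 summary of changes repeats the general sentence without an exception. The SAP says nothing about palifosfamide dosing.

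**The concern.** The general sentence sets no condition beyond a treatment-related palifosfamide delay. A neutrophil count that misses the retreatment threshold because of palifosfamide causes exactly such a delay, and it also meets the ANC row. One instruction then reduces the dose and the other keeps it.

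Two things depend on which is followed: the dose of a cytotoxic drug at the next cycle, and the subject's remaining allowance under the two-reduction cap. Safety and tolerability is a primary objective, and Arm C tests a combination whose dose justification (the appendix to the Amendment 2 summary) stresses the balance between palifosfamide cytotoxicity and immune induction. If sites resolve the conflict differently, Arm C subjects with the same toxicity will receive different regimens for no clinical reason. The synopsis plans about 30 centers and at most 26 Arm C subjects, so 26/30 ≈ 0.87 per center on average. Few sites would build up a settled practice.

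**Working it through.** There is no stated figure to reproduce. The check is a comparison of the text with each row of Table 3, followed by simple dose arithmetic.

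**Step 1: where text and table disagree**

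| Table 3 row | Table action | Against the 80% sentence |
|---|---|---|
| Platelets below 100 × 10⁹/L | Delay, reduce 20% | Agrees |
| ANC below 1500/mm³ | Delay, keep dose | **Conflicts** |
| Neutropenic fever | Delay, reduce 20% | Agrees |
| Any Grade 4 hematologic toxicity | Delay, reduce 20% | Agrees |
| eGFR fall of 25% to under 50% | Hold for repeat test; reduce 20% if confirmed | Agrees |
| eGFR fall of 50% or more | Hold for repeat test; discontinue if confirmed | Differs, if a hold counts as a delay |
| Non-hematologic Grade 3 and Grade 4 | Delay, reduce 20% | Not comparable: both rows are labeled not treatment-related, so the sentence does not govern them |

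The ANC row is the only one that delays and then restarts at full dose. Febrile neutropenia and Grade 4 hematologic toxicity have rows of their own that match the text, and most subjects with a treatment-related Grade 4 event leave treatment anyway. The conflict is therefore limited to treatment-related neutropenia that is afebrile and below Grade 4.

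**Step 2: one such delay, from the starting dose**

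- Text: 0.80 × 120 = 96 mg/m²/day; 3 × 96 = 288 mg/m² per cycle; 1 of 2 reductions used.
- ANC row: 120 mg/m²/day; 3 × 120 = 360 mg/m² per cycle; 0 of 2 used.
- Difference: 120 − 96 = 24 mg/m²/day; 360 − 288 = 72 mg/m² per cycle.

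**Step 3: two such delays, before different cycles**

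This assumes that a reduction carries forward. The protocol does not say whether a second 20% is taken from the current or the starting dose, so both are shown.

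- Text, second 20% of the current dose: 120 × 0.8 × 0.8 = 76.8 mg/m²/day.
- Text, second 20% of the starting dose: 120 × 0.6 = 72 mg/m²/day.
- In both cases 2 of 2 reductions are used.
- ANC row: 120 mg/m²/day, 0 of 2 used.

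**The case against.** The best reply is that the general sentence cites Table 3, so a reader is sent to the row for the event and finds an explicit instruction to keep the dose. On that view the 80% is a default and the table gives the specifics. The opposite reading works poorly: it would leave the ANC instruction with no effect for palifosfamide-related neutropenia, which is what the table is titled for. It would also sit badly with the row that discontinues palifosfamide for a confirmed eGFR fall of at least 50%. This is persuasive about intent. But the pointer comes directly after the 80% figure and can equally be read as a citation supporting it. No wording makes the table an exception to the sentence or sets an order of precedence.

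It is also fair to say that the consequences are limited. Both instructions wait for ANC to recover to 1500, and neither exceeds the planned 120 mg/m²/day, so no overdose follows from either reading. The two-delay figures need two qualifying events with the text followed both times. The unclear base for a second reduction is a separate ambiguity, which also affects rows where text and table agree. The one-delay comparison is therefore the figure to rely on. None of this removes the mismatch.

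**Conclusion.** The concern holds. For an Arm C subject with treatment-related, afebrile neutropenia below Grade 4, section 6.2.5 prescribes both 96 and 120 mg/m²/day for the next cycle, and both one and none of the two permitted reductions. The first figure assumes that the subject is still at the starting dose.

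After two such delays the doses would be 72 to 76.8 versus 120 mg/m²/day, under the assumptions stated with that calculation. The documents give no frequency for these delays and none is assumed, so the effect on average dose in Arm C cannot be stated.

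This is an internal inconsistency in a dosing rule. The sample size, the Simon boundaries and the definition of the 16-week PFS rate do not depend on it. It should be fixed because a cytotoxic dose should not rest on each site inferring the intent.

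**What to change.** Reword the general sentence in 6.2.5 so that Table 3 controls, for example:

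*If treatment-related toxicity delays palifosfamide, give palifosfamide at 80% of the dose in the next cycle unless Table 3 specifies otherwise.*

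The ANC row then stands as written. This wording also names palifosfamide where the present sentence refers to study treatment as a whole. That is a deliberate second change: in Arm C, study treatment includes INXN-1001 and INXN-2001, and the sentence that follows in 6.2.5 already confines modification to the drug responsible when the AE is clearly related to one drug and not the other.

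If the clinical team does intend a reduction after ANC delays, leave the sentence and end the ANC row with a 20% reduction instead. That choice is clinical.

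The cost is one sentence or one table cell in a protocol clarification, with no change to sample size, boundaries, visits or data collection.
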